11.5 Study Stopping Guidance

If any of the events listed, other than myocarditis/pericarditis, in Section 12.8.2.2 Ad hoc DSMB Reviews occur, the Data Safety Monitoring Board (DSMB) chair will be notified, and a review of safety data will be performed to determine if consent of potential participants, randomization/allocation, and/or administration of investigational study medication should be halted. If 2 weeks has elapsed and the DSMB has not met, then no new participants will be consented, allocated, or randomized until after the DSMB completes review of the safety data.

For any NCI-CTCAE Grade 2 or higher myocarditis or pericarditis that occurs within 6 weeks of vaccine administration, the DSMB chair be notified of the event within 3 business days from when the AESI was reported to DAIT/NIAID (see Section 12.5.2). The DSMB chair will adjudicate whether an expedited, ad hoc safety review by the full DSMB is required.

12. Safety Monitoring and Reporting

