Study Stopping Rules	
If any of the events listed below occur, other than myocarditis/pericarditis, the DSMB chair will be notified, and a review of safety data will be performed to determine if enrollment in the study, randomization/allocation, and/or administration of investigational study medication should be halted. If two weeks has elapsed and the DSMB has not met, then no new participants will be consented, allocated or randomized until after the DSMB completes review of the safety data.
 
For any NCI-CTCAE Grade 2 or higher myocarditis or pericarditis that occurs within 6 weeks of vaccine administration, the DSMB chair be notified of the event within 3 business days from when the AESI was reported to DAIT/NIAID (see Section 12.5.2). The DSMB chair will adjudicate whether an expedited, ad hoc safety review by the full DSMB is required.
 
Adult Participants:
 
Any of the following adverse events in adult participants attributable to the vaccine will trigger an ad hoc DSMB Safety Review:
 
• Death related to vaccine.• Life-threatening adverse event (Grade 4) related to vaccine.• Permanent or severe disability related to vaccine.• Occurrence of a Grade 3 or higher, vaccine-related SAE of the same type in 3 or more of the study participants who have received a study treatment. Note: Only SAEs occurring within 24 weeks of a Day 1 visit will be counted.• Occurrence of a Grade 2 or higher myocarditis or pericarditis within 6 weeks of vaccine administration. Note: the DSMB chair will be notified within 3 business days from when the AESI is reported to DAIT/NIAID.• Occurrence of severe flare or relapse after an additional homologous COVID-19 vaccine dose given at Stage 1, defined as within 12 weeks of the Stage Baseline/Week 0 visit (vaccination), in 3 of the first 10 participants or 30% thereafter.• Occurrence of severe flare or relapse after a subsequent alternative COVID-19 vaccine dose given at Stage 2, defined as within 12 weeks of the Stage 2 Baseline/Week 0 visit (vaccination), in 3 of the first 10 participants or 30% thereafter. 
Pediatric Participants:
 
Any of the following adverse events in pediatric participants attributable to the vaccine will trigger an ad hoc DSMB Safety Review:
 
• Death related to vaccine• Life-threatening AE (Grade 4) related to vaccine• Permanent or severe disability related to vaccine• Occurrence of a Grade 3 or higher, vaccine-related SAE of the same type in 3 or more of the study participants who have received a study

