12.5.3.2 Expedited Safety Reporting

This option, with 2 possible categories, applies if the AE is classified as one of the following:

Category 1: Serious and unexpected suspected adverse reaction [SUSAR] (see Section 12.2.1.1 Suspected Adverse Reaction (SAR) and Section 12.2.1.2 Unexpected Adverse Event or Unexpected Suspected Adverse Reaction and 21 CFR 312.32(c)(1)i).

The sponsor shall report any SAR that is both serious and unexpected. The sponsor shall report an AE as a SAR only if there is evidence to suggest a causal relationship between the study drug and the AE, such as:

- A single occurrence of an event that is uncommon and known to be strongly associated with drug exposure (e.g., angioedema, hepatic injury, or Stevens-Johnson Syndrome);
- One or more occurrences of an event that is not commonly associated with drug exposure but is otherwise uncommon in the population exposed to the drug (e.g., tendon rupture);
- An aggregate analysis of specific events observed in a clinical trial (such as known consequences of the underlying disease or condition under investigation or other events that commonly occur in the study population independent of drug therapy) that indicates those events occur more frequently in the drug treatment group than in a concurrent or historical control group.

Category 2: Any findings from studies that suggest a significant human risk

The sponsor shall report any findings from other epidemiological studies, analyses of AEs within the current study or pooled analysis across clinical studies or animal or in vitro testing (e.g., mutagenicity, teratogenicity, carcinogenicity) that suggest a significant risk in humans exposed to the drug that would result in a safety-related change in the protocol, informed consent, and investigator brochure or package insert or other aspects of the overall conduct of the study.

DAIT/NIAID shall notify the FDA and all participating investigators of expedited Safety Reports within 15 calendar days; unexpected fatal or immediately life-threatening suspected adverse reaction(s) shall be reported as soon as possible or within 7 calendar days.

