- b. New, recurrent or worsening neurological symptoms accompanied by corresponding objective worsening on neurologic examination with an increase of any one of the following in MS participants compared to the immediate prior assessment:
 - i. ≥ 0.5 step(s) on the Expanded Disability Status Scale (EDSS), or
 - ii. ≥ 2 points on one Functional Systems Score (FSS), or
 - iii. ≥ 1 point on two or more FSS.

Episodic spasms, sexual dysfunction, fatigue, mood change, or bladder or bowel urgency or incontinence will not suffice to establish a relapse. Sexual dysfunction and fatigue will not contribute to the EDSS or FSS for assessing MS relapse.

- **Pemphigus:** 3 or more new lesions a month that do not heal spontaneously within 1 week or by the extension of established lesions in a participant who has achieved disease control.

After review of the safety data, the DSMB will make recommendations regarding study conduct, including modifications and/or continuation. The DSMB will recommend and DAIT/NIAID, as Sponsor, will determine whether protocol changes should be implemented and/or whether and when consenting, allocation, randomization, and vaccinations can resume.

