12.8.2.2.3 Temporary Suspension of Randomization/Allocation and Vaccinations

Section 11.5 Study Stopping Guidance outlines the procedure for DSMB ad hoc review due to the events listed in Section 12.8.2.2 Ad hoc DSMB Reviews. If during the ad hoc review, the DSMB determines that a temporary halt in randomization/allocation is required, participants who received vaccination prior to the temporary halt will continue in the study as planned. During the halt in randomization/allocation, recruitment, screening and consenting may continue, but no additional study vaccine doses will be administered.

13. Statistical Considerations and Analytical Plan

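### The automatic pause after two weeks without a DSMB meeting covers consent, allocation and randomization but not vaccination of participants already assigned

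*Protocol*

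**What the plan says.** Protocol Section 11.5 has two steps. First, a trigger event leads to notification of the DSMB chair and a safety review, which decides whether consent, randomization/allocation or dosing stops. Dosing is named there: the review asks whether "administration of investigational study medication should be halted". Second, there is an automatic fallback: "If 2 weeks has elapsed and the DSMB has not met, then no new participants will be consented, allocated, or randomized", lasting until the review is finished. Dosing is absent from this second list.

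The Study Stopping Rules row of the protocol synopsis has the same fallback: "then no new participants will be consented, allocated or randomized until after the DSMB completes review of the safety data". The SAP's protocol summary (Section 3, Study Stopping Rules) also lists only these three activities.

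The explicit stop on doses is in Section 12.8.2.2.3, headed "Temporary Suspension of Randomization/Allocation and Vaccinations". It applies if "the DSMB determines that a temporary halt in randomization/allocation is required" during the ad hoc review. In that case "recruitment, screening and consenting may continue, but no additional study vaccine doses will be administered". Sections 12.8.2.2.1 and 12.8.2.2.2 end by saying that, after the DSMB's recommendation, the sponsor decides "whether and when consenting, allocation, randomization, and vaccinations can resume".

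Myocarditis and pericarditis are carved out of the two-week rule and go to the chair by a separate route. This point concerns the other triggers.

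**The concern.** The fallback exists for one situation: a trigger has occurred and the DSMB has not met for two weeks. The triggers include vaccine-related death, a vaccine-related Grade 4 event and permanent or severe disability. In that situation the rule stops three administrative steps and leaves out the activity that exposes participants to vaccine. Someone randomized or allocated shortly before the pause can reach Baseline during it, and no rule tells the site to hold the dose.

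The surrounding text suggests a drafting omission. Dosing appears in the sentence just before the fallback. Vaccinations are among the activities that the sponsor may allow to resume, and they are in the heading of Section 12.8.2.2.3. No reason is given for leaving them out of the fallback.

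**Working it through.** No statistical figure is involved. The check is on scope, then on whether the affected group can exist.

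**1. Scope of each rule**

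| Text | What brings it into force | Consent | Assignment | Dosing |
|---|---|---|---|---|
| 11.5, review sentence | Outcome of the safety review | may be halted | may be halted | may be halted |
| 11.5 fallback; synopsis; SAP Section 3 | 2 weeks with no DSMB meeting | stopped | stopped | not mentioned |
| 12.8.2.2.3 | DSMB determination during the ad hoc review | may continue | stopped | stopped |

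The third row cannot apply when the second begins, because the second presupposes that the DSMB has not met. The Baseline vaccine-eligibility checks (Sections 8.1.3, 8.2.4, 8.4.4) concern the individual participant and do not refer to a study pause.

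**2. Open arms with a minimum interval between assignment and dose**

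- Pediatric Stage 1 (Table 7): 10 arms, of which 8 are in Cohorts A and B and 2 in Cohort C.
- Adult Stage 2 (Table 5): 12 arms − 3 closed Janssen arms = 9.
- Pediatric Stage 2 (Table 9): 6.
- Open arms: 10 + 9 + 6 = 25. All Adult Stage 1 arms are closed.

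Randomization must be at least 7 days before the dose in Pediatric Stage 1 Cohorts A and B (Section 8.3.1). In Stage 2, allocation belongs to Screening, which is at least 7 days before the dose for new recruits and rollovers (Sections 8.2.1, 8.2.3, 8.4.1, 8.4.3). Arms with the 7-day minimum: 8 + 9 + 6 = 23.

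**3. Who is undosed when the pause starts**

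Let a be the day of assignment and P the day the pause starts. The dose falls on day a + 7 or later. If a is within the last 7 days before P, then a + 7 > P, so everyone assigned in those 7 days in the 23 arms is still undosed.

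Let w be the days from Screening (for rollovers, from when the screening data were obtained) to assignment. Dosing must fall within 28 days of that starting point, so the last permitted day is a + (28 − w). With the 7-day minimum, w can be at most 28 − 7 = 21. For someone assigned the day before the pause:

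- earliest dose: 7 − 1 = 6 days into the pause;
- latest dose: 28 − w − 1 days into the pause, which is 6 for w = 21, 13 for w = 14, and 27 for w = 0. The last is a theoretical bound, because eligibility needs a central-laboratory antibody result.

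**4. Room for a delayed dose**

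From the earliest permitted dose to the 28-day limit there are (28 − w) − 7 = 21 − w days: 14 for w = 7, 7 for w = 14, none for w = 21. These values of w are illustrations; the protocol sets no minimum.

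**5. Medication holds already begun (Section 7.1.1)**

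- Methotrexate: required hold 7 + 7 = 14 days, cap 21, so at most 21 − 14 = 7 days of dose delay without a restart.
- MMF/MPA: planned hold 3 + 10 = 13 days, no stated cap. A delay of 7, 14 or 21 days without a restart gives 20, 27 or 34 days off drug.

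The sentences that allow an immediate restart cover only participants found ineligible for the dose. They do not cover someone whose dose is paused.

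**The case against.** Four arguments on the other side have weight.

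*There are other ways to stop dosing.* Under Section 12.8.2.1 the chair is told of IND Safety Reports so as to be able to recommend protocol suspension, and the medical monitor or protocol co-chairs can bring events of concern to the DSMB. Under Section 12.5.3.2, "unexpected fatal or immediately life-threatening suspected adverse reaction(s) shall be reported as soon as possible or within 7 calendar days", and investigators are among those notified, so they should often know of such an event before two weeks are up. This lowers the likelihood of harm. It does not supply an automatic rule, since each decision to stop doses remains discretionary.

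*Section 12.8.2.2.3 may already cover it.* It refers back to Section 11.5, and its dosing stop applies during a halt in randomization/allocation, which the fallback arguably is. That reading is possible, but the preceding sentence ties the halt to a DSMB determination, so the narrower reading is stronger. A safety rule should not depend on which one a site adopts.

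*It may be deliberate.* Assigned participants may have stopped medication for the dose, and the triggers include a 30% severe-flare rule as well as deaths. But Section 12.8.2.2.3 makes no exception for such participants when the DSMB orders a halt, and the protocol gives no reason for treating the fallback differently.

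*The gap is only residual.* The plan already allows consent, assignment and dosing during the first two weeks. That is correct; the point concerns the period from the start of the pause until a DSMB determination.

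A reader might also infer a contradiction over consenting, because Section 11.5 stops it and Section 12.8.2.2.3 lets it continue. The second is permissive and the first prohibitive, so both can be obeyed.

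**Conclusion.** The point holds as a gap in the rule. Followed literally, the automatic pause does not hold doses for participants already assigned, and no other text does so without someone's decision. It is worth fixing because the triggers are serious and the change is small.

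The size can be given only in structure: 23 of 25 open arms have at least 7 days between assignment and dose, so while enrollment is active some participants will be assigned and undosed when a pause starts. Their number cannot be derived, because neither document gives an accrual rate. The timing takes the start of the pause as given; Section 11.5 does not say whether the two weeks run from the event, its report or the chair's notification.

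Two stronger readings are not supported. A reader might infer that the protocol authorizes dosing during the pause; it is silent. A reader might infer that dosing could not be stopped before the DSMB meets; the chair can recommend suspension, and the sponsor and investigators can stop voluntarily.

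**What to change.** 1. In Section 11.5, the synopsis and the SAP summary, add study vaccine administration to the activities that stop automatically, with the same end point: completion of the DSMB's review.
2. State that participants whose dose is paused may restart withheld methotrexate or MMF/MPA immediately, as those found ineligible at Baseline already may.
3. State that the 28-day dosing limit still applies. If the dose cannot be given in time, the existing rules follow: rescreening or replacement for Stage 1 participants and Stage 2 new recruits, and return to the previous schedule for rollovers.

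I would not add an instruction to repeat the medication hold before a rescheduled dose. A 7-day pre-dose hold, a restart and then a new 7 + 7 days comes to 7 + 14 = 21 days, which already reaches the methotrexate cap if it is cumulative. A new 7-day hold may also not fit the 21 − w days left before the 28-day limit.

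The cost goes beyond wording if the DSMB is late. Some assigned participants, including some randomized children in Pediatric Stage 1 Cohorts A and B, will pass the 28-day limit and be rescreened, replaced or returned to their previous schedule. Doses of products not involved in the event are delayed too, which matches the scope of the existing pause on consent and assignment. If leaving dosing open is intended, the protocol should say so and give the reason.

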12.1 Overview

This section defines the types of safety data that will be collected under this protocol and outlines the procedures for appropriately collecting, grading, recording, and reporting those data. Adverse events that are classified as serious according to the definition of health authorities must be reported promptly (per Section 12.5 Reporting Adverse Events and Serious Adverse Events to Sponsor (DAIT/NIAID) to the Sponsor (DAIT/NIAID). Appropriate notifications will also be made to site principal investigators, Institutional Review Boards (IRBs), and the FDA.

Information in this section complies with International Conference on Harmonisation (ICH) Guideline E2A: Clinical Safety Data Management: Definitions and Standards for Expedited Reporting, ICH Guideline E6(R2) Good Clinical Practice: Integrated Addendum to ICH E6(R2), and 21CFR Parts 312 and 320, and applies the standards set forth in the National Cancer Institute (NCI), Common Terminology Criteria for Adverse Events (CTCAE), Version 5.0 (https://ctep.cancer.gov/protocolDevelopment/electronic_applications/ctc.htm#ctc_50).

12.2 Definitions

12.2.1 Adverse Event (AE)

Any untoward or unfavorable medical occurrence associated with the use of an intervention in humans, whether or not considered intervention related (see 21 CFR 312.32(a)).

An AE can be any unfavorable and unintended sign (e.g., an abnormal laboratory finding), symptom, or disease temporally associated with the use of a drug and does not imply any judgment about causality. An AE can arise with any use of the drug (e.g., off-label use or in combination with another drug) and with any route of administration, formulation, or dose, including an overdose.

12.2.1.1 Suspected Adverse Reaction (SAR)

A suspected adverse reaction (SAR) is any AE for which there is a reasonable possibility that the investigational drug [or investigational study therapy regimen] caused the AE. For the purposes of safety reporting, 'reasonable possibility' means there is evidence to suggest a causal relationship between the drug and the AE. An SAR implies a lesser degree of certainty about causality than adverse reaction, which means any AE caused by a drug (21 CFR 312.32(a)).

12.2.1.2 Unexpected Adverse Event or Unexpected Suspected Adverse Reaction

An AE or SAR is considered "unexpected" if it is not listed in the investigator brochure or is not listed at the specificity or severity that has been observed; or, if an investigator brochure is not required or available, is not consistent with the risk information described in the general investigational plan or elsewhere in the current application, as amended.

12.2.1.3 Solicited Adverse Events (Reactogenicity)

Solicited AEs are predefined local and systemic events for which the participants will be specifically questioned, and which will be noted by these participants. In this study, queried symptoms will include:

- Injection site reaction such as pain, erythema, induration/edema as well as development of papules, and ulceration.
- Axillary lymphadenopathy.
- Solicited systemic reactions including fever (assessed as daily oral temperature), chills, myalgia, arthralgia, fatigue*, headache*, nausea*, vomiting, hives, and diarrhea.

*Participants that are 2-3 years old will have sleepiness, irritability/crying, and loss of appetite assessed rather than fatigue, headache, and nausea.

- Increased shortness of breath, chest pain**, swelling/pain in arm or leg**.

**These symptoms will be assessed in participants age 5 years and above.

- Increase in symptoms of the participant's underlying autoimmune disease.

12.2.2 Unsolicited Adverse Event

For the purpose of this protocol, an AE is considered “unsolicited” when it is collected through an open-ended question and it is not specified as a solicited AE.

12.2.3 New-onset Chronic Medical Condition (NOCMC)

A NOCMC is defined as any new International Statistical Classification of Diseases and Related Health Problems (ICD) diagnosis that is applied to the study participant during the course of the study, after receipt of the vaccine, that is expected to continue for at least 3 months and requires continued health care intervention.

12.2.4 Medically Attended Adverse Event

Medically attended adverse event (MAAE) is defined as a hospitalization, emergency room visit, or an otherwise unscheduled visit to or from medical personnel for any reason that is considered possibly related or related to study vaccine.

12.2.5 Adverse Events of Special Interest

Adverse events of special interest (AESIs) include the following:

- Myocarditis (probable and confirmed cases)
- Pericarditis

See Appendix 20.8 for cases definitions of probable and confirmed myocarditis and pericarditis according to the Centers for Disease Control and Prevention (CDC) criteria

In addition, the following AESI will be collected in the arms in which the Sanofi-GSK COVID-19 Vaccine is administered.

- New onset of potential immune-mediated diseases (pIMDs).

See Appendix 20.7. Disease flares of the underlying autoimmune disease, including new manifestation of the disease will not be captured as an AESIs. Disease flares should be reported following Section 12.4.2 Increase in Autoimmune Disease Activity.

pIMDs are a subset of AEs that include autoimmune diseases and other inflammatory and/or neurologic disorders of interest which may or may not have an autoimmune etiology. AEs that need to be recorded and reported as pIMDs, including those listed in Appendix 20.7.

However, the Investigator will exercise their medical and scientific judgment in deciding whether other diseases have an autoimmune origin (that is pathophysiology involving systemic or organ-specific pathogenic autoantibodies) and should also be recorded as a pIMD. When there is enough evidence to make any of the diagnoses mentioned in Appendix 20.7 the AE must be reported as a pIMD. Symptoms, signs or conditions which might (or might not) represent the above diagnoses, should be recorded and reported as AEs but not as pIMDs until the final or definitive diagnosis has been determined, and alternative diagnoses have been eliminated or shown to be less likely.

12.2.6 Serious Adverse Event (SAE)

An AE or SAR is considered “serious” if, in the view of either the investigator or Sponsor (DAIT/NIAID), it results in any of the following outcomes (21 CFR 312.32(a)):

1. Death.

2. A life-threatening event: An AE or SAR is considered “life-threatening” if, in the view of either the investigator or Sponsor [add DAIT/NIAID or other Sponsor, *if applicable*], its occurrence places the participant at immediate risk of death. It does not include an AE or SAR that, had it occurred in a more severe form, might have caused death.
3. Inpatient hospitalization or prolongation of existing hospitalization.
4. Persistent or significant incapacity or substantial disruption of the ability to conduct normal life functions.
5. Congenital anomaly or birth defect.
6. Important medical events that may not result in death, be life threatening, or require hospitalization may be considered serious when, based upon appropriate medical judgment, they may jeopardize the participant and may require medical or surgical intervention to prevent one of the outcomes listed above.

Elective hospitalizations or hospital admissions for the purpose of conduct of protocol-mandated procedures are not to be reported as an SAE unless hospitalization is prolonged due to complications.

